Appendix B: Presentation of Data and Programming Specifications

General

- Specialized text styles, such as bold, italics, borders, and shading will not be used in tables, figures, and data listings unless they add significant value to the table, figure, or data listing.
- Only standard keyboard characters are to be used in tables and data listings.
- Special characters, such as nonprintable control characters, printer-specific, or font-specific characters, will not be used on a table, figure, or data listing.
- Hexadecimal character representations are allowed (e.g., μ , α , β).
- All footnotes will be left justified and at the bottom of a page. Footnotes must be used sparingly and must add value to the table, figure, or data listing.

Tables

- Formal organization of tabulations may be changed during programming, if appropriate, e.g., tables for the different variables may be combined into a single table, or tables with more than 1 variable may be split into several tables.
 - Means and medians will be presented to 1 more decimal place than the raw data. Standard deviations will be presented to 2 more decimal places than the raw data. Minimums and maximums will be reported with the same number of decimal places as the raw data.
 - Percentages will be presented to the tenths place.
 - For frequency counts of categorical variables, categories whose counts are zero will be displayed for the sake of completeness. For example, if none of the subjects discontinue due to “lost to follow-up,” this reason will be included in the table with a count of 0. Categories with zero counts will not have zero percentages displayed.
 - Lower and upper confidence interval values must be presented to 1 decimal place more than the raw/derived data (i.e., to the same number of decimal places as the mean).
 - Percentiles (e.g., 25%, 75%) must be presented to 1 decimal place more than the raw/derived data.
 - For all inferential analyses, P values will be rounded to 4 decimal places (or at the highest level of precision) with a leading zero (0.0001). P values less than 0.0001 will be presented as “<0.0001.”
 - The last footnotes will be
 - “Source: xxx”, where xxx indicates the source **table number(s)** if applicable (in case aggregated results like mean or median are plotted) or the source listing(s) (in case individual responses are plotted) and/or source dataset(s) (e.g., AdaM).
 - “PROGRAM SOURCE: ...\\xx.sas, DATA CUT OFF DATE: DDMMYYYY, RUN DATE: DDMMYY hh:mm”.
- where extract date (e.g., data cut off, database lock) is the date stamp of the data snapshot used.

Figures

- Legends will be used for all figures with more than 1 variable or item displayed. Treatment group sizes (n=xx) will be included, as appropriate.
 - Figures will be in black and white but can be in color to add value to the clarity and readability of a figure. Lines must be wide enough to see the line after being copied.
 - For box plots, the horizontal line will represent the median, + represents the group mean, the length of the box represents the interquartile range (25th-75th percentiles), and the whiskers will represent the minimum and maximum.
 - The last footnotes will be
 - “Source: xxx”, where xxx indicates the source listing number(s) and/or source dataset(s) (e.g., AdaM).
 - “PROGRAM SOURCE: ...\\xx.sas, DATA CUT OFF DATE: DDMMYYYY, RUN DATE: DDMMYY hh:mm”.
- where extract date (e.g., data cut off, database lock) is the date stamp of the data snapshot used.

Listings

- Formal organization of the listing may be changed during programming, if appropriate, e.g., additional variables may be included, change in the column order, or the listing may be split into multiple parts due to space constraints.
 - If not otherwise specified, all data listings will be sorted by sequence/treatment, center, subject number, visit, and date/time, as appropriate.
 - All date values will be presented in a SAS date (e.g., 29AUG2001) format.
 - All observed time values will be presented using a 24-hour clock HH:MM:SS format (e.g., 01:35:45 or 11:26). Seconds will only be reported if they were measured as part of the study.
 - The last footnote will be
 - “PROGRAM SOURCE: ...\\xx.sas, DATA CUT OFF DATE: DDMMYYYY, RUN DATE: DDMMYY hh:mm”.
- where extract date (e.g., data cut off, database lock) is the date stamp of the data snapshot used.

Missing or incomplete dates (i.e., AEs, concomitant medications, and start dates of current molluscum episode and initial diagnosis)

The most conservative approach will be systematically considered. If the AE onset date is missing/incomplete, it is assumed to have occurred during the study treatment phase (i.e., considered a TEAE) except if the partial onset date or other data, such as the stop date, indicates differently. Similarly, a medication with partial start and stop dates could be considered as both a prior and concomitant treatment.

The following algorithms will be applied to missing and incomplete start and stop dates:

Start Dates

- If the day portion of the start date is missing, then the start date will be estimated to be equal to the date of first application of study drug, provided the start month and year are the same as the first application of study drug and the stop date is either after the first application of study drug or completely missing. Otherwise, the missing day portion will be estimated as “01.”
- If both the day and month portions of the start date are missing, then the start date will be estimated to be equal to the date of first application of study drug, provided the start year is the same as the first application of study drug and the stop date is either after the first application of study drug or completely missing. Otherwise, the event will be assumed to start on the first day of the given year (e.g., ??-??-2013 is estimated as 01-JAN-2013) or the subject’s date of birth, whichever is latest.
- If the start date is completely missing and the stop date is either after the application of study drug or completely missing, the start date will be estimated to be the first day of study drug application. Otherwise, the start date will be estimated to be the first day of the same year as the stop date or the subject’s date of birth, whichever is latest. All other non-AE and non-concomitant medication day calculations where only partial dates are available will be handled as follows: the first day of the month will be used in the calculations if the day part of a start date is missing while January 1 will be employed if both the month and day parts of a start date are missing.

Stop Dates

- If only the day of resolution is unknown, the day will be assumed to be the last day of the month (e.g., ??-JAN-2013 will be treated as 31-JAN-2013).
- If both the day and month of resolution are unknown, the event will be assumed to have ceased on the last day of the year (e.g., ??-??-2013 will be treated as 31-DEC-2013).
- If the stop date is completely missing and the event is not continuing, the event will be assumed to be after first application of study drug and will be imputed using the last known date on the study.

For the start dates of current molluscum episode and initial diagnosis, the day will be estimated as “01” if only day is missing. If both month and day are missing, then it will be estimated as “01-JUN-YYYY” or the subject’s date of birth, whichever is latest.

If the start date of current molluscum episode is partial, then the following imputation will be made:

- If only the day is unknown, the day will be assumed to be the first day of the month or the date of birth, whichever is later.
- If the day and month are missing, then the start date will be estimated to be June 1st or the date of birth, whichever is later.

Standard Calculations

Variables requiring calculation will be derived using the following formulas:

- **Days** – A duration expressed in days between 1 date (date1) and another later date (date2) is calculated using the formulas noted below:
Duration in days = date2 – date1 + 1.
- **Months** – A duration expressed in months will be calculated as (later date – earlier date + 1)/(30.4167).
- **Years** – A duration expressed in years will be calculated as (later date – earlier date + 1)/(365).
- **Change from Baseline** – Change from Baseline will be calculated as follows:
Change from Baseline = postbaseline value – baseline value.
- **Percent change from Baseline** – Change from Baseline will be calculated as follows:
Percent change from Baseline = (postbaseline value – baseline value)/baseline value
× 100.

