9.3 Demographic and Baseline Characteristics

Demographic variables include age, sex, ethnicity, and race. Age will be calculated in years relative to the informed consent date.

Other baseline characteristics include lesion counts at baseline, site type (dermatologist vs other), number of sites and a breakdown of site type, number of randomly assigned subjects in household (1 subject vs 2 subjects), number of households and breakdown of household size, age at and time since initial clinical diagnosis of the current molluscum episode and age at and time since onset of symptoms of current molluscum episode. Descriptive statistics will be presented for ages and other continuous variables. Frequency counts and percentages will be presented for sex, ethnicity, race and other categorical variables. Demographic and baseline characteristics will be summarized for the Safety, ITT, and PP Populations.

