10.6 Examination of Subgroups

Subgroup analyses of complete clearance at Week 12 for investigator type (dermatologist vs other) and household number of randomized subjects (1 subject per household vs 2 subjects per household), and will be presented in a forest plot for the ITT Population. An additional subgroup analysis of complete clearance at Week 12 for age (<1 year old, ≥ 1 to <2 years old, ≥ 2 to <6 years old, ≥ 6 to <12 years old, ≥ 12 to <18 years old, ≥ 18 years old) and onset of MC symptoms duration prior to baseline (≤ 6 months vs >6 months) will be summarized descriptively for the ITT Population.

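### A molluscum onset or diagnosis known only by year is set to 1 June with no upper bound, so it can fall after the recorded diagnosis or after Baseline

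*Combined protocol and SAP*

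**What the plan says.** The final SAP is the version whose table shells are numbered 3.0. Its Appendix B, under missing or incomplete dates, gives two overlapping rules for molluscum dates.

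- The first is introduced by "For the start dates of current molluscum episode and initial diagnosis" and so covers both dates. A missing day becomes the first of the month. For year-only dates it continues "If both month and day are missing, then it will be estimated as" 1 June of that year, or the date of birth if that is later.
- The second covers onset only and repeats the year-only rule: "then the start date will be estimated to be June 1st or the date of birth, whichever is later". Its day-only branch has a birth floor, which the first rule's day-only branch lacks.

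Neither rule limits the imputed date to the diagnosis, Screening, randomization or Baseline, and neither requires onset to be on or before diagnosis.

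The dates are used in two places. SAP section 9.3 reports age at and time since diagnosis, and "age at and time since onset of symptoms of current molluscum episode". SAP section 10.6 splits Week 12 clearance by "onset of MC symptoms duration prior to baseline" at 6 months, a split that "will be summarized descriptively for the ITT Population". Duration is not among the covariates of the primary model in SAP section 10.3.

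**The concern.** An episode cannot begin after it was diagnosed, and a subject who qualifies with 3 to 70 lesions at Baseline (Protocol 5.2) cannot have an onset after Baseline. Both later dates are collected, yet the rule ignores them. Year-only onsets are plausible: Protocol 6.2.1 takes the start of the episode from when the subject or caregiver first noticed it, and the SAP writes a rule for the case.

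At stake are impossible entries in a baseline table and, in some records, a subgroup assignment contradicted by a date already in the database.

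**Working it through.** The plan states no figure that this rule produces, so there is nothing to reproduce. The inputs are the 1 June rule and the duration formula in Appendix B ("A duration expressed in months will be calculated as" the later date minus the earlier date plus one day, divided by 30.4167) and the 6-month cut in section 10.6. Six months is 6 × 30.4167 = 182.5 days. The calendar dates below are examples; the documents do not give enrolment dates.

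**Route 1: 1 June falls after a known diagnosis.** This happens for any year-only onset with a diagnosis from 1 January to 31 May of that year, whatever the enrolment calendar. Take onset 2019, diagnosis 15 February 2019, Baseline 16 September 2019:

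- Imputed onset is 1 June 2019, which is 106 days after the diagnosis.
- Imputed duration: (107 + 1)/30.4167 = 3.55 months, so the subject goes into the group of 6 months or less.
- Duration proven by the diagnosis: (213 + 1)/30.4167 = 7.04 months, so the subject belongs in the group over 6 months.

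The certain subgroup error needs diagnosis to Baseline over 6 months while 1 June to Baseline is 6 months or less. For a 2019 onset this confines Baseline to 2 July through 29 November 2019:

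- 1 January to 2 July: 183/30.4167 = 6.02 months.
- 1 June to 29 November: 182/30.4167 = 5.98 months.

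If Baseline is in a later calendar year than the onset, the imputed duration is at least 215/30.4167 = 7.07 months (1 June to 1 January). The subject is then in the over-6-months group anyway, and only the onset/diagnosis order is wrong.

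**Route 2: 1 June falls after Baseline.** This needs a year-only date in the Baseline year and a Baseline before 1 June. Take onset 2019 and consent and Baseline on 10 May 2019:

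- Computed as Baseline minus onset plus one: (−22 + 1)/30.4167 = −0.69 months.
- Computed literally as later minus earlier plus one: (22 + 1)/30.4167 = +0.76 months, a spurious positive value that looks valid.
- Under either reading, age at onset exceeds age at consent.

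This route does not change the subgroup. The longest possible true duration, 1 January to 31 May 2019, is 151/30.4167 = 4.96 months (5.00 in 2020). Enumerating every onset and Baseline day gave 0 misclassified of 7,821 combinations for 2019 (Baselines from 27 March, the day after the protocol date) and 0 of 11,628 for 2020.

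**Illustrative frequency.** Assume that every year-only onset is in the Baseline year and uniform from 1 January to Baseline, that every diagnosis date is fully known and uniform between onset and Baseline, and that Baselines are uniform over the stated window. Simulating 200,000 records per window gives:

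| Baseline window, 2019 | After Baseline | After diagnosis | Proven subgroup error |
|---|---|---|---|
| April to September | 33% | 61% | about 1% |
| June to December | 0% | 30% | about 4% |

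If 3% to 10% of 340 subjects (10 to 34) had year-only onsets, the proven subgroup errors would number 0.01 × 10 = 0.1 to 0.04 × 34 = 1.4 subjects. With onset uniform over the prior year instead, about 6% fall after diagnosis, none after Baseline, and none give a proven subgroup error.

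**The case against.** The strongest objection is that nothing inferential depends on these dates. That is correct: the subgroup is descriptive, it is not one of the forest-plot factors, and duration is not in the primary or secondary model.

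It could also be said that programmers would catch an impossible date. The SAP gives them no authority to change it. The clause in Appendix B that lets other data override an imputed date is written for adverse event onset only, and double programming checks agreement with the rule, not the sense of the rule.

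A reader might infer more than the documents support:

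- *That a sizeable number of subjects is affected.* Multiplying 30% to 61% by all year-only subjects would suggest roughly 3 to 21 onsets after diagnosis. Those rates hold only for onsets in the Baseline year, whereas recall by year may well refer to an earlier year. They also assume a complete diagnosis date; if both dates are known only by the same year, both become 1 June and do not conflict. No count can be derived.
- *That the missing Baseline bound causes subgroup errors.* It does not; only a known earlier diagnosis does.
- *That durations will be negative.* The formula read literally gives a false positive value instead. Either is wrong.
- *That onsets after Baseline will occur.* This needs Baselines before 1 June. The protocol is dated 26 March 2019, so they are possible, but the documents do not show them.

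**Conclusion.** The rule is wrong as written: it can replace a year-only date with one that a recorded diagnosis or the Baseline visit rules out. The diagnosis route rests on the text and the calendar alone; the Baseline route also needs a Baseline before 1 June. The result is impossible values for age at and time since onset or diagnosis and, through the diagnosis route only, an occasional subject in the wrong 6-month group.

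The number affected cannot be computed, because neither enrolment dates nor the rate of year-only dates is given. For the subgroup it is probably very small, and the figure of 0.1 to 1.4 subjects is itself an upper scenario because it puts every year-only onset in the Baseline year. The primary and secondary conclusions do not change. This is a minor correction, worth making because it costs almost nothing.

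**What to change.** In Appendix B, impute a year-only onset as the earliest of 1 June of that year, the known diagnosis date and the Screening/Baseline date, but not before birth. Cap an imputed diagnosis date at Screening/Baseline in the same way. Merge the two onset rules into one, so that the day-only branch has a single treatment of the birth floor.

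In the route 1 example, onset becomes 15 February 2019, the duration 7.04 months, and the subgroup is right. In the route 2 example, onset becomes 10 May 2019 and the duration one day (0.03 months); the subgroup stays at 6 months or less.

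A plain cap is enough. Replacing 1 June by a midpoint between 1 January and the earliest known later date would be a different imputation method, because it also moves records where 1 June breaks no bound. With diagnosis and Screening both on 16 September 2019, for example, it would shift onset to about 10 May. Nor does a cap remove the ordinary error of a 1 June guess when no earlier diagnosis date is known, and it need not.

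The cost is a sentence or two in Appendix B and a small change to the derivation. No new data are needed. Made before unblinding, it avoids an ad hoc programming decision or an analysis that SAP section 6 would class as post hoc.

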Appendix C: SAS Programming QC Requirements

Derived datasets are independently programmed by two programmers. The separate datasets produced by the 2 programmers must match 100%. Detailed specifications for the derived datasets are documented in the study analysis dataset specifications provided to the client at study conclusion.

Tables are independently reprogrammed by a second programmer for numeric results. Listings are checked for consistency against corresponding tables, figures, and derived datasets. Figures are checked for consistency against corresponding tables and listings, or independently reprogrammed if there are no corresponding tables or listings.

The entire set of TLFs is checked for completeness and consistency prior to its delivery to the client by the lead biostatistician and a senior level, or above, reviewer.

Appendix D: List of Tables, Figures, and Listings

The following proposal for section 14 and 16.2 is completed according to ICH E3 guidelines. The ICH heading numbers and description are in **bold**. Minor changes from this planned index do not need to be amended in the SAP.

Formal organization of tabulations may be changed during programming, if appropriate, e.g., tables for the different variables may be combined into a single table, or tables with more than 1 variable may be split into several tables.

The shells for the outputs below are contained in the file titled “Novan NI-MC301 SAP TLFs Version 3.0”.

TABLES, FIGURES, AND GRAPHS

Table Number	Table Title	Analysis Population
14	TABLES, FIGURES, AND GRAPHS REFERRED TO BUT NOT INCLUDED IN THE TEXT	
14.1	DEMOGRAPHIC DATA	
14.1.1.1	Subject Disposition	Enrolled
14.1.1.2	Enrollment by Site	ITT
14.1.2.1	Demographic and Baseline Characteristics	Safety
14.1.2.2	Demographic and Baseline Characteristics	ITT
14.1.2.3	Demographic and Baseline Characteristics	PP
14.1.3.1	Study Drug Exposure	Safety
14.1.3.2	Study Drug Compliance	Safety
14.1.4	Significant and Major Protocol Deviations	ITT
14.1.5	Medical History	ITT
14.1.6.1	Prior Medications	ITT
14.1.6.2	Concomitant Medications	ITT
14.2	Efficacy data	
14.2.1.1	Complete Clearance Lesion Count Response at Week 12	ITT
14.2.1.2	Complete Clearance Lesion Count Response at Week 12	PP

Table Number	Table Title	Analysis Population
14.2.1.3	Sensitivity Analysis: Complete Clearance Lesion Count Response at Week 12	ITT
14.2.1.4	Sensitivity Analysis: Complete Clearance Lesion Count Response at Week 12	PP
14.2.1.6	Proportion of Subjects with Complete Clearance at Week 12 by Subgroup	ITT
14.2.1.7	Dropout Sensitivity Analysis: Complete Clearance Lesion Count Response at Week 12	ITT
14.2.1.8	One Subject Per Household Sensitivity Analysis: Complete Clearance Lesion Count Response at Week 12	ITT
14.2.1.9	Exploratory Analysis of the Variability of Treatment Effect of Complete Clearance Lesion Count Response at Week 12 Across Pools of at Least 17 Subjects	ITT
14.2.1.10	Exploratory Analysis of the Variability of Treatment Effect of Complete Clearance Lesion Count Response at Week 12 Across Pools of at Least 10 Subjects	ITT
14.2.2.1	Complete Clearance Lesion Count Response at Week 8	ITT
14.2.2.2	Complete Clearance Lesion Count Response at Week 8	PP
14.2.3.1	Complete Clearance Lesion Count Response at Weeks 2 and 4	ITT
14.2.3.2.1	Summary of a 95% Reduction in Lesion Counts from Baseline Response by Visit	ITT
14.2.3.2.2	Summary of a 90% Reduction in Lesion Counts from Baseline Response by Visit	ITT
14.2.3.2.3	Summary of a 75% Reduction in Lesion Counts from Baseline Response by Visit	ITT
14.2.3.3.1	Percent Change from Baseline in Lesion Count by Visit	ITT
14.2.3.4.1	Change from Baseline in Lesion Count by Visit	ITT
14.2.3.5	Summary of Recurrence after Complete Clearance	ITT
14.2.3.6.1	Kaplan-Meier Estimates of Time to Complete Clearance (Days) from Start of Dosing	ITT
14.2.3.7	Summary of Scarring and Keloid by Visit	ITT
14.2.3.8.1	Summary of the Dermatology Life Quality Index (DLQI) and Subscales by Visit	ITT
14.2.3.8.2	Summary of the Dermatology Life Quality Index (DLQI) Individual Questions by Visit	ITT
14.2.3.8.3.1	Summary of the Children's Dermatology Life Quality Index (CDLQI) and Subscales by Visit	ITT
14.2.3.8.3.2	Summary of the Children's Dermatology Life Quality Index (CDLQI) and Subscales by Visit	ITT: Complete Responders at Week 12
14.2.3.8.3.3	Summary of the Children's Dermatology Life Quality Index (CDLQI) and Subscales by Visit	ITT: Subjects with at least a 95% Reduction in

Table Number	Table Title	Analysis Population
		Lesion Counts at Week 12
14.2.3.8.3.4	Summary of the Children's Dermatology Life Quality Index (CDLQI) and Subscales by Visit	ITT: Subjects with at least a 90% Reduction in Lesion Counts at Week 12
14.2.3.8.3.5	Summary of the Children's Dermatology Life Quality Index (CDLQI) and Subscales by Visit	ITT: Subjects who did not Achieve Complete Clearance at Week 12
14.2.3.8.4	Summary of the Children's Dermatology Life Quality Index (CDLQI) Individual Questions by Visit	ITT
14.2.3.9	Summary of Increase in Subject-Reported Spread to Household Members by Visit	ITT
14.2.3.10.1	Summary of Lesion Counts by Highest Dichotomized BOTE Score	ITT
14.2.3.10.3	Percent Change from Baseline in Lesion Count over Time by Dichotomized Week 2 BOTE Score	ITT
14.2.3.10.4	Summary of Complete Clearance by Visit and Dichotomized Week 2 BOTE Score	ITT
14.2.3.10.5	Summary of the Beginning of the End (BOTE) Inflammation Score Results by Visit	Safety
14.3	Safety data	
14.3.1	Displays of Adverse Events	
14.3.1.1	Overall Summary of Treatment-Emergent Adverse Events	Safety
14.3.1.2	Summary of Treatment-Emergent Adverse Events by System Organ Class and Preferred Term	Safety
14.3.1.3	Summary of Treatment-Emergent Adverse Events by System Organ Class, Preferred Term, and Maximum Severity	Safety
14.3.1.4	Summary of Treatment-Emergent Adverse Events by System Organ Class, Preferred Term, and Relationship to Study Drug	Safety
14.3.1.5	Summary of Serious Treatment-Emergent Adverse Events by System Organ Class and Preferred Term	Safety
14.3.1.6	Summary of Treatment-Emergent Adverse Events Leading to Study Drug Discontinuation by System Organ Class and Preferred Term	Safety

Table Number	Table Title	Analysis Population
14.3.1.7	Summary of Treatment-Emergent Adverse Events Leading to Death by System Organ Class and Preferred Term	Safety
14.3.2	Listings of deaths, other serious and significant adverse events	
14.3.2.1	Listing of Serious Adverse Events	Safety
14.3.2.2	Listing of Adverse Events Leading to Study Drug Discontinuation	Safety
14.3.2.3	Listing of Deaths	Safety
14.3.6	Other safety data	
14.3.6.1.1	Summary of Local Skin Reaction (LSR) Composite Score by Visit	Safety
14.3.6.1.2	Summary of Local Skin Reaction (LSR) Score Results by Visit	Safety
14.3.6.1.3	Shift Summary of Local Skin Reaction (LSR) Score Results by Visit	Safety
14.3.6.2	Summary of Events of Special Interest	Safety
14.3.6.3	Summary of Physical Examination Findings	Safety
14.3.6.4	Summary of Patch Testing Results	Safety

Figure Number	Figure Title	Analysis Population
14.2.1.5	Forest Plot: Odds Ratio (95% CI) of the Proportion of Subjects with Complete Clearance at Week 12	ITT
14.2.3.3.2	Percent Change from Baseline in Lesion Count over Time by Treatment Group	ITT
14.2.3.4.2	Mean Change from Baseline in Lesion Count over Time by Treatment Group	ITT
14.2.3.6.2	Kaplan-Meier Plot of Time to Complete Clearance (Days) from Start of Dosing	ITT
14.2.3.10.2	Plot of Complete Clearance at Week 12 by Highest Dichotomized Categorized BOTE Score	ITT

Section 16.2: List of Data Listings

ICH Listing Number	Listing Title	Analysis Population
16.1.7	Subject Randomization	ITT
16.2	SUBJECT DATA LISTINGS	
16.2.1	Discontinued subjects	
16.2.1.1	Subject disposition	Enrolled
16.2.2	Protocol deviations	
16.2.2.1	Protocol Deviations	ITT
16.2.2.2	Inclusion/Exclusion Criteria	Enrolled
16.2.3	Subjects excluded from the efficacy analysis	
16.2.3.1	Analysis Populations	Enrolled
16.2.4	Demographic data	
16.2.4.1	Demographic and Baseline Characteristics	ITT
16.2.4.2	Patch Testing Consent/Assent	Enrolled
16.2.4.3	Medical History	ITT
16.2.4.4	Prior and Concomitant Medications	ITT
16.2.5	Compliance and/or drug concentration data	
16.2.5.1	Study Drug Administration	Safety
16.2.5.2	Study Drug Accountability	Safety
16.2.5.3	Treatment Adjustment	Safety
16.2.5.4	Treatment Compliance	Safety
16.2.6	Individual efficacy response data	
16.2.6.1	Lesion Counts	ITT
16.2.6.2	Lesion Count Derived Efficacy Variables and Time to Complete Clearance	ITT
16.2.6.3	Scarring/Keloid Assessment	ITT
16.2.6.4	Dermatology Life Quality Index (DLQI) and Subscales	ITT
16.2.6.5	Children's Dermatology Life Quality Index (CDLQI) and Subscales	ITT
16.2.6.6	Household Transmission	ITT
16.2.7	Adverse events listings	

ICH Listing Number	Listing Title	Analysis Population
16.2.7.1	All Adverse Events	Safety
16.2.8	Listing of individual laboratory measurements by subject, when required by regulatory authorities	
16.2.8.1	Urine Pregnancy Test	Safety
16.2.9	Other data	
16.2.9.1	Beginning-of-the-End (BOTE) Inflammation Score	Safety
16.2.9.2	Local Skin Reactions (LSR)	Safety
16.2.9.3	Physical Examination	Safety
16.2.9.4	Patch Testing	Safety
16.2.9.5	Telephone Contact	ITT
16.2.9.6	Subjects who Require a Narrative	ITT
